## **An Open-Label Trial of Triheptanoin in Patients with Glucose Transporter Type-1 Deficiency Syndrome (GLUT1 DS)**

### **1.0 GOALS AND OBJECTIVES**

- 1.1 The primary objective of the study is:
- To evaluate the safety of triheptanoin via adverse event rates and laboratory values.
- 1.2 The secondary objective of the study is:
- To evaluate the long-term efficacy of triheptanoin as measured by the change in seizure frequency from historical baseline.

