## **4.0 SELECTION AND ENROLLMENT OF SUBJECTS**

### **4.1 Inclusion Criteria**

Individuals eligible to participate in this study must meet all of the following criteria:

- 1) Patients with GLUT1 DS by physician diagnosis
- 2) Males and females, aged 1 to 50 years
- 3) Allowed to be on concomitant AEDs
- 4) Patients are able to tolerate triheptanoin if they have been (or are currently being) treated with this medication
- 5) Must, in the opinion of the investigator, be willing and able to comply with study procedures and schedule
- 6) Provide written assent (if appropriate) and written informed consent by a Legally Authorized Representative (LAR) after the nature of the study has been explained, and prior to any research-related procedures
- 7) Sexually active subjects must be willing to use an acceptable method of contraception while participating in the study
- 8) Females of childbearing potential must have a negative pregnancy test at Screening and be willing to have additional pregnancy tests during the study

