##### 5.4.4.2 Laboratory

Blood samples will be collected for CBC, Chem-7, ALT/AST, at Screening, Week 13, and every six months through the end of year 2, and annually thereafter for all subjects.

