## **10.0 DATA COLLECTION AND ADVERSE EXPERIENCE REPORTING**

### *10.1 Clinical Data Collection*

Data to be collected will include demographic features (gender, age, ethnicity and race), GLUT1 DS medical history, prior and concomitant medications and therapies, details of the 3-day diet record and seizure count from the daily patient diary, and results obtained at each office visit (weight, height, vitals, physical examination, and labs). In addition, data will be collected on adverse events. The entire list of variables and explanations can be found in the Data Dictionary.

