### 11.0 STATISTICAL CONSIDERATIONS

#### 11.1 *Safety Analysis*

Safety data will be reviewed annually or more frequently, as needed, by another physician investigator familiar with the disorder and treatment. For the safety analysis, the numbers (frequency) and incidence rates of AEs and SAEs will be summarized during exposure to triheptanoin throughout the study. The analyses of safety will include all subjects who receive any triheptanoin during the study and provide any post-treatment safety information. All AEs will be coded using the Medical Dictionary for Regulatory Activities (MedDRA). The incidence and frequency of AEs will be summarized by System Organ Class (SOC), Preferred Term (PT), relationship to study drug, and severity. A by-subject listing will be provided for those subjects who experience a SAE, including death, or experience an AE associated with early withdrawal from the study or study drug treatment.

Clinical laboratory data will be summarized by the type of laboratory test. The frequency and percentage of subjects who experience abnormal clinical laboratory results (i.e., outside of reference ranges) and/or clinically significant abnormalities after study drug administration will be presented for each clinical laboratory measurement. For each clinical laboratory measurement, descriptive statistics will be provided for Baseline and all subsequent scheduled visits during which laboratory measurements were obtained. Changes from Baseline to the treatment visits will also be provided. Descriptive statistics of vital signs and concomitant medications will be provided in a similar manner.

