**TABLE 1: SCHEDULE OF EVENTS– SUBJECTS PREVIOUSLY ON AND CONTINUING ON TRIHEPTANOIN**

| Name of Visit   | Screening       | Initial Treatment |             |             |            | Extension | End of Study or Termination |
|---|-----------------|-------------------|-------------|-------------|------------|-----------|-----------------------------|
|   | Screening Visit | Visit 1           | Visit 2, 3  | Visits 4-6  | Visits 7-8 | Visit 9   |                             |
| Timepoint   | -14 days        | Day 1             | Week 13, 26 | Every 6 mos | Annually   | Annually  |                             |
| Informed Consent
a) LAR
b) Assent   | X               |                   |             |             |            |           |                             |
| Demographics  | X               |                   |             |             |            |           |                             |
| GLUT1 DS Medical History  | X   |                   |             |             |            |           |                             |
| Prior and Concomitant Medications & Therapies                                       | X               | X                 | X           | X           | X          | X         | X                           |
| Adverse Events  | X               | X                 | X           | X           | X          | X         | X                           |
| Dietician Consult 
(including 3-day diet record review)              |                 | X                 | X           | X           | X          | X         | X                           |
| Daily Patient Diary Review: Seizure Count   | X               | X                 | X           | X           | X          | X         | X                           |
| Weight and vitals   | X               | X                 | X           | X           | X          | X         | X                           |
| Physical Examination    | X               | X                 | X           | X           | X          | X         | X                           |
| Labs
a) CBC 
b) Chemistry                             | X               |                   | X           | X           | X          | X         | X                           |

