**Subjects currently or previously treated with triheptanoin**

1 GLUT1-DS History, patients must have been confirmed via historical test or by physician diagnosis

2 Three-day diet diaries are to be reviewed with the dietician or study staff upon each indicated visit.

3 Weight (kg). Vitals includes blood pressure (mm Hg), heart rate in beats per minute, respiration rate in breaths per minute and temperature in degrees Celsius (°C), and should be performed at the beginning of each visit before additional assessments are completed.

4 Physical Examination: HEENT, neck, respiratory-auscultation of lungs.

5 CBC panel: Hematocrit, hemoglobin, platelet, RBC, WBC.

6 Chemistry panel:sodium, potassium, chloride, bicarbonate or CO2, blood urea nitrogen (BUN), creatinine, glucose, ALP, ALT (or SGPT), AST (or SGOT), total bilirubin, GGT, albumin, total protein, calcium.

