**Subjects currently or previously treated with triheptanoin**

7 GLUT1-DS History, patients must have been confirmed via historical test or by physician diagnosis

2 Three-day diet diaries are to be reviewed with the dietician or study staff upon each indicated visit.

9Discuss continued completion of seizure diary.

10 Weight (kg). Vitals includes blood pressure (mm Hg), heart rate in beats per minute, respiration rate in breaths per minute and temperature in degrees Celsius (°C), and should be performed at the beginning of each visit before additional assessments are completed.

11 Physical Examination: HEENT, neck, respiratory-auscultation of lungs.

12 CBC panel: Hematocrit, hemoglobin, platelet, RBC, WBC.

13 Chemistry panel:sodium, potassium, chloride, bicarbonate or CO2, blood urea nitrogen (BUN), creatinine, glucose, ALP, ALT (or SGPT), AST (or SGOT), total bilirubin, GGT, albumin, total protein, calcium.

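### Section 5.4.4.2 and the schedule footnotes specify different chemistry panels, and Section 11.1's single change-from-Baseline summary does not separate subjects already on triheptanoin at Screening from naive subjects

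*Combined protocol and SAP*

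**What the plan says.** The primary objective is "To evaluate the safety of triheptanoin via adverse event rates and laboratory values".

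**Panel.** Section 5.4.4.2 states "Blood samples will be collected for CBC, Chem-7, ALT/AST, at Screening, Week 13", and then gives the later visits. Footnotes 6 (Table 1) and 13 (Table 2) itemise a chemistry panel that runs from sodium to "blood urea nitrogen (BUN), creatinine, glucose, ALP, ALT (or SGPT), AST (or SGOT), total bilirubin, GGT, albumin, total protein, calcium". Section 10.1 adds "The entire list of variables and explanations can be found in the Data Dictionary"; that dictionary is not among the documents.

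**Baseline.** Section 11.1 defines one safety set of treated subjects with post-treatment safety data. It plans laboratory descriptives at Baseline and at each scheduled laboratory visit, and then "Changes from Baseline to the treatment visits will also be provided". It does not define Baseline or mention schedule or prior exposure. Tables 1 and 2 place a laboratory draw at Screening and none at Visit 1.

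**Exposure at entry.** Table 1 is for "SUBJECTS PREVIOUSLY ON AND CONTINUING ON TRIHEPTANOIN". Inclusion criterion 4 reads "Patients are able to tolerate triheptanoin if they have been (or are currently being) treated with this medication". Schedule B subjects are naive and are titrated from the start of treatment (Section 5.4.2).

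**Weight.** Section 7.2 names weight gain as an adverse drug reaction. Section 11.1 covers vital signs but does not name weight. The schedule tables have a combined weight-and-vitals row, but its footnotes state weight apart from the vitals. Section 10.1 lists height at office visits; neither schedule table does.

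**The concern.** There is no control arm, so change from a pre-treatment value is the main quantitative evidence of a laboratory effect. Two things can weaken it.

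First, analytes that are not drawn cannot be recovered later. Four of the six at issue (ALP, total bilirubin, GGT, albumin) are liver-related, and Section 2.2.1 reports hepatic steatosis in a nine-month rat study.

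Second, a Screening value means different things in different subjects. In a naive subject, later change reflects starting the drug. In a subject already taking it, later change reflects only continued exposure. In one undivided table the second group can mask a change in the first, and in a safety study that error runs toward reassurance.

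The analysis is descriptive, so the risk is a misread table, not a wrong test decision.

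**Working it through.** The plan states no power, effect size or expected laboratory change, so there is no figure of its own to reproduce.

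**1. Panels side by side**
- Section 5.4.4.2: Chem-7 (sodium, potassium, chloride, bicarbonate, BUN, creatinine, glucose; the usual seven, which the documents do not define) plus ALT and AST: 7 + 2 = 9.
- Footnotes 6 and 13: those 9 plus ALP, total bilirubin, GGT, albumin, total protein and calcium: 15.
- Difference: 15 − 9 = 6. The shorter list lies wholly inside the longer one.

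**2. Dilution in a combined table**

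Let q be the share of subjects on drug at Screening. The documents give no Schedule A/B split, so q is assumed. Suppose those subjects show no further mean change and all others show the full change d. Then the combined mean change is (1 − q) × d.

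| q | Share of d remaining | d = 0.5 SD reads as |
|---|---|---|
| 0.2 | 80% | 0.40 SD |
| 0.5 | 50% | 0.25 SD |
| 0.8 | 20% | 0.10 SD |

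The same holds for shifts. A 20% rate of new abnormality in naive subjects, with none in the on-drug group, would read as 16, 10 or 4%.

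**3. Why schedule alone is not the right split**

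Suppose Schedule A is 20, 50 or 80% of subjects but only half of it is on drug at Screening. Then q = 0.1, 0.25 or 0.4, and 90, 75 or 60% of d remains in the combined table. In a table for Schedule A alone, (1 − 0.5) × d = 0.5d remains, which is still half diluted. The relevant variable is drug status at Screening.

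**4. Precision**

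Take 50 subjects, d = 0.5 SD and within-subject correlation 0.7 (both assumed). The variance of change within a group is 2(1 − 0.7) = 0.6 SD². The combined table adds q(1 − q)d².
- All of Schedule A on drug: combined estimate/SE is 3.54, 2.17, 0.88. Schedule B alone (40, 25, 10 subjects) gives 4.08, 3.23, 2.04.
- Half of Schedule A on drug: combined 4.03, 3.30, 2.61, against the same 4.08, 3.23, 2.04.

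Separation therefore makes the change interpretable; it does not always make it more precise.

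**5. Weight**

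Assume growth of 2–4 kg a year in children and none in adults. Over five years that is 10–20 kg in a child, or a pooled mean of 5–10 kg if half the subjects are children, with no drug effect.

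**The case against.** A reader might infer that 11.1 commits to pooling and so builds in a bias toward no effect. The documents do not go that far. Section 11.1 never says the schedules are combined, and the rest of the protocol keeps them apart. What stands is that one set and one summary are described, with no separation stated.

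Nor is Baseline fixed as Screening. Section 5.4 lets screening data recorded before consent stand in for new screening, and 11.2 uses a pre-triheptanoin historical rate, though only for seizures. This supports asking for a definition.

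Zero further change in on-drug subjects is assumed, and it drives the dilution figures. Late or cumulative change over up to five years is a legitimate question, which is a reason to label that group and keep it.

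The naive group is not a clean comparison either. Section 5.4 contemplates patients still on a ketogenic diet with the screening period waived, while exclusion criterion 2 refers to the time of drug initiation. A naive subject's Screening draw could therefore precede a diet change as well as the drug. Maturation over five years also affects laboratory values.

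On the panel, drawing the footnote list satisfies both texts, so loss of analytes is a risk and not a certainty. The Data Dictionary may list the analytes, but the two protocol texts would still differ.

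It is also tempting to call the count of out-of-range and/or clinically significant results an error. It is not. Any cumulative count rises with the number of draws, the wording can mean two presentations, and 11.1 already plans statistics by visit. Nor does weight gain go unanalysed: reported events enter the AE tables, and the combined row may bring weight under vital signs.

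**Conclusion.** Two points hold.

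The panel conflict is on the face of the text: six chemistry analytes appear in the footnotes and not in 5.4.4.2, given the usual meaning of Chem-7.

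The change-from-Baseline plan is under-specified for a population that may be partly on drug at its only scheduled pre-treatment draw. If it is carried out as one table, and if on-drug subjects change little further, the mean change shrinks in proportion to their share, to between 80 and 20% of the true change over the range examined. The split, the effect size and the correlation are assumptions. That the two kinds of change would be mixed in a single table does not depend on them.

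The weight point is minor. If weight is summarised with vital signs, raw kilograms in subjects enrolled from age 1 are confounded by growth.

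**What to change.** 1. Reconcile Section 5.4.4.2 with footnotes 6 and 13, so that one itemised panel applies at every laboratory visit.
2. In 11.1, define laboratory Baseline. Present change and Screening-to-visit shifts separately by triheptanoin status at Screening: naive, previously treated but off drug, and on drug. Take the status from the prior and concomitant medication record already scheduled. Label the on-drug group as continued-exposure change. Use a documented pre-triheptanoin value as a supplementary baseline where one exists. Flag naive subjects whose Screening draw was taken on a ketogenic diet.
3. Name a weight analysis: age- and sex-standardised change against a stated reference in children, kilograms in adults. Add height to both schedule tables to match 10.1.
4. Optional: report out-of-range and clinically significant results in separate rows.

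The cost is a text amendment and modest table programming, with no added visits or blood draws. The downside is small cells. At an observed 20% abnormal, the exact 95% interval is 10–34% for 10/50, 7–41% for 5/25 and 3–56% for 2/10.

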#### 11.2 *Efficacy Analysis*

For efficacy analysis, seizure frequency expressed as the number per month will be calculated during treatment and compared to the historical seizure rate prior to treatment with triheptanoin. Change from baseline will be expressed as median percent reduction in baseline seizure frequency.

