## 5.4 Study Procedures

The dose will be ~35-40% of total caloric intake (~1-4 g/kg/day, depending on age), for up to 5 years, including the extension period, with a visit to the clinical site at day 1, Months 3, 6, 12, 18, 24, and annual thereafter for both groups. Enrolled subjects are otherwise able to maintain standard of care treatment which may include anti-epileptic drugs (AEDs) throughout the duration of the study.

Up to 50 patients with a diagnosis of GLUT1DS who have or have not been previously on Triheptanoin will be enrolled based on their prior treatment status.

During a two-week screening period, subjects will record daily seizures and diet (last three days) in a diary to serve as a baseline measurement. If a patient has recorded all screening criteria prior to consent, that data may be used in lieu of additional screening. If, in the opinion of the Investigator, a patient who is currently on the ketogenic diet would be placed at potential risk for compromise of patient safety by stopping ketogenic diet for two weeks before initiation of treatment protocol, the two-week screening period from consent to initiation may be waived by the Investigator. In the instance of waiving the screening period, seizure and diet information will be gathered retrospectively via parent/patient interview. After the Screening period, subjects will enter the treatment period on one of two protocol schedules. Study Visit window will be +/- 2 weeks from the scheduled date.

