### 7.3 *Efficacy*

Seizure frequency: The number of observable seizures will be recorded once per day, via diary by patient or caregiver

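### The pre-triheptanoin seizure rate that Section 11.2 uses as comparator has no stated source or window in the protocol text, and the Section 5.4 screening diary cannot supply it for Schedule A subjects on drug at screening

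*Combined protocol and SAP*

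**What the plan says.** The secondary objective (Section 1.2) is the "change in seizure frequency from historical baseline". Section 11.2 expresses seizure frequency per month on treatment, to be "compared to the historical seizure rate prior to treatment with triheptanoin", and continues: "Change from baseline will be expressed as median percent reduction in baseline seizure frequency". It does not say whether the baseline in that sentence is the historical rate or another count.

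The other places where a seizure count is described are these:

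- Section 5.4, for the two-week screening period: "subjects will record daily seizures and diet (last three days) in a diary to serve as a baseline measurement". This covers all subjects. Records made before consent may replace it. If screening is waived for a patient on ketogenic diet, a retrospective interview takes its place.
- Section 7.3: "The number of observable seizures will be recorded once per day, via diary by patient or caregiver".
- Section 10.1 lists GLUT1 DS medical history, but the only seizure count it lists is in "details of the 3-day diet record and seizure count from the daily patient diary". It adds: "The entire list of variables and explanations can be found in the Data Dictionary".
- The Table 1 note on medical history: "GLUT1-DS History, patients must have been confirmed via historical test or by physician diagnosis".

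On treatment status at entry, inclusion criterion 4 (Section 4.1) admits patients now taking triheptanoin, Section 5.4.1 has previously treated subjects carry on dosing, and the title of Table 1 describes its population as continuing on the drug. No washout is stated.

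**The concern.** This is a single-arm study, so the baseline is the only comparator for efficacy, and Section 11.2 describes the only efficacy analysis. A rate per month needs a count and a period of observation. The visible text supplies neither for the time before triheptanoin, except where the screening diary happens to cover it.

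It does so for naive subjects. It does not for Schedule A subjects who are on drug at screening. For them an analyst must find a count that the protocol text does not describe, or fall back on the diary that Section 5.4 calls a baseline. The first course leaves the window open, so two analysts could reach different results. The second compares drug with drug and pulls the pooled median toward zero.

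**Working it through.** The plan gives no seizure rate, effect size, power calculation or split between schedules, so there is no figure of its own to reproduce. The check is a comparison of the passages, followed by an illustration of size.

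**Can each described count serve as a pre-triheptanoin rate?**

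| Count | Stated window | Before triheptanoin? |
|---|---|---|
| Screening diary, naive subjects (5.4) | 14 days | Yes, but 11.2 does not name it as comparator |
| Screening diary, Schedule A subjects on drug (5.4, 5.4.1) | 14 days | No |
| Pre-consent records (5.4) | As for screening | Possibly; not required |
| Waiver interview (5.4) | None | Not required |
| GLUT1 DS medical history (10.1, Table 1) | None | Not stated; the note covers diagnosis only |

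For Schedule A subjects on drug, no row is certain to give the comparator.

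**Illustration of size.** The limit of 50 subjects is from Section 3.2. Everything else is assumed: 20 previously treated subjects on drug at screening and 30 naive; untreated rates lognormal (log-SD 1) around a stated median per 30 days; Poisson counts; nine 14-day treatment windows; a true reduction of 50%. For each subject,

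percent reduction = 100 × (1 − on-treatment rate / baseline rate).

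This is undefined when the baseline count is zero, so those subjects are dropped.

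*Case 1: Section 11.2 is followed.* All baselines are pre-drug, so there is no on-drug dilution and only the window for the 20 previously treated subjects varies. Naive subjects keep their 14-day diary.

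| Median rate per 30 days | Pooled median, 14-day window | Pooled median, 84-day window | Difference (points) | Zero baselines among the 20 (14 v 84 days) |
|---|---|---|---|---|
| 2 | 62.5% | 56.9% | 62.5 − 56.9 = 5.6 | 8.0 v 1.2 |
| 5 | 53.4% | 51.9% | 53.4 − 51.9 = 1.5 | 3.7 v 0.2 |
| 20 | 49.6% | 49.9% | 49.6 − 49.9 = −0.3 | 0.5 v 0.0 |

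Short windows overstate the reduction at low rates because subjects with a chance count of zero drop out and those with chance high counts remain. Within the 20 alone the medians are 61.6% against 51.0% at 2 a month, but Section 11.2 as written implies one pooled median, where the effect is smaller.

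*Case 2: the on-drug diary is used for the 20.* Their baseline and on-treatment rates are then the same in expectation, so their true percent change is 100 × (1 − 1) = 0.

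| Median rate per 30 days | Pooled median, 20 of 50 on drug | Pooled median, none on drug |
|---|---|---|
| 5 | 45.0% | 53.3% |
| 20 | 37.8% | 49.8% |
| 60 | 39.4% | 49.8% |

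At 20 a month the shortfall is 49.8 − 37.8 = 12.0 points. If the effect varies between subjects (SD 20 points), the diluted medians are 45.4%, 34.6% and 31.9%.

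The share on drug matters most. A separate set of assumptions (median 30 a month, log-SD 0.8, eight windows, true reduction 50%) gives about 49.5%, 44%, 30% and −1% with 0%, 25%, 50% and 100% of subjects on drug.

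**The case against.** The strongest reply is that Sections 1.2 and 11.2 agree: the comparator is historical and precedes triheptanoin, and Section 5.4 never names the diary as the efficacy baseline. This stands. A reader might infer that the plan compares drug with drug in Schedule A and so dilutes the efficacy result. The documents do not support that: Case 2 arises only if the analyst departs from Section 11.2.

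A second reply is that the rate may be defined elsewhere. Section 10.1 refers to a Data Dictionary for the full list of variables, and the Table 1 note does not limit what medical history may record. This also stands. A reader might infer that the historical rate is never collected. That cannot be concluded without the Data Dictionary, only that the protocol text does not say so.

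A third reply is that pre-consent records may replace the screening diary. For some Schedule A subjects these could pre-date triheptanoin. They need not, so the gap narrows but does not close.

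Finally, the result is secondary and descriptive, with no test, in a study whose primary objective is safety. That limits the weight of the point. It does not tell an analyst which count to use.

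**Conclusion.** The point holds in this form. The protocol text requires a pre-triheptanoin seizure rate and gives it no source or window. The diary that Section 5.4 provides as a baseline cannot be that rate for Schedule A subjects on drug at screening. It would be too strong to say that naive subjects are wholly unaffected: their diary is suitable, but Section 11.2 does not name it, and in the illustration about 12 of the 30 have a zero 14-day count at 2 a month.

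The size depends on which course the analyst takes. Following Section 11.2, the open window is worth about 6 points at 2 seizures a month and 2 points or less at 5 or more. Falling back on the diary costs about 12 points at 20 a month with 20 of 50 on drug. Every rate, effect and split behind these figures is assumed. The change is worth making because this is the only efficacy analysis described; nothing here bears on the primary safety objective.

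**What to change.** In Sections 5.4 and 11.2, state that the efficacy baseline is the seizure rate per 30 days before any triheptanoin, and give its source:

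- Naive subjects: the screening diary, or pre-consent records that pre-date triheptanoin.
- Previously treated subjects: prior-trial or chart counts over a fixed window ending before the first triheptanoin dose.

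Add a CRF field for this rate if the Data Dictionary has none. State that a diary recorded on triheptanoin is not used as the baseline for percent reduction, and that subjects without a pre-triheptanoin count contribute only their on-study rate. Report the median percent reduction, n and the number of zero-baseline subjects separately for Schedules A and B. Give the waiver interview a fixed recall window.

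The cost is wording in two sections, at most one CRF field, and abstraction from charts or prior-trial records. The downside is smaller denominators: some Schedule A subjects may have no percent reduction.

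### The efficacy baseline is described in two ways that conflict for subjects already on triheptanoin, and the only efficacy summary, a median percent reduction, is undefined for subjects with no baseline seizures

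*Combined protocol and SAP*

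**What the plan says.** The secondary objective in section 1.0 is "To evaluate the long-term efficacy of triheptanoin as measured by the change in seizure frequency from historical baseline". Section 11.2 is the whole efficacy analysis. Monthly seizure frequency on treatment is "compared to the historical seizure rate prior to treatment with triheptanoin", and "Change from baseline will be expressed as median percent reduction in baseline seizure frequency". It gives no source or length for the historical rate and no rule for a subject whose baseline is zero.

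Section 5.4 describes a two-week screening period in which "subjects will record daily seizures and diet (last three days) in a diary to serve as a baseline measurement". Two substitutes are allowed:
- Records made before consent: "If a patient has recorded all screening criteria prior to consent, that data may be used in lieu of additional screening".
- Recall: "seizure and diet information will be gathered retrospectively via parent/patient interview". This applies only when the investigator waives screening because stopping the ketogenic diet for two weeks could put the patient at risk.

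The seizure-related entry condition in section 4.1 is only "Patients with GLUT1 DS by physician diagnosis". Neither 4.1 nor 4.2 asks for a minimum seizure count. Section 4.1 also admits patients already taking the drug: "Patients are able to tolerate triheptanoin if they have been (or are currently being) treated with this medication". Section 5.4.1 and the title of Table 1 have Schedule A subjects continuing their dose.

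**The concern.** There are two separate gaps.

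First, the baseline. A pre-triheptanoin rate and a screening diary could be the same thing for a naïve subject. They cannot be the same for a Schedule A subject who is on drug while filling in the diary. An analyst who takes the diary as baseline compares treatment with treatment for those subjects.

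Second, the zero baseline. Percent reduction divides by the baseline, so a subject with no baseline seizures has no value. The natural reading is to leave such subjects out. With a short baseline and infrequent seizures, those left in are the ones who happened to seize in that window. Their later counts fall back towards their usual rate, and this looks like a benefit.

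With a single arm, neither artefact can be told apart from a drug effect in the reported median.

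**Working it through.** The documents give no seizure rate, effect size or power figure, so there is no stated number to reproduce. All rates below are assumptions, given as means per month.

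**Inputs from the protocol.** Up to 50 subjects (section 3.2). A 14-day screening diary (5.4). Treatment windows of 14 days after Visit 1 and 14 days before each of Visits 2–9 (5.4.4.1 and the visit list): 1 + 8 = 9 windows, or 9 × 14 = 126 days.

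**Share with a zero baseline.** For Poisson counts at rate r per month over d days, P(0) = exp(−r × d/30.44). With d = 14:
- r = 1: exp(−0.460) = 0.63
- r = 2: exp(−0.920) = 0.40
- r = 4: exp(−1.840) = 0.16
- r = 8: exp(−3.679) = 0.025

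With r = 1 and d = 84 it is exp(−2.760) = 0.06.

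**Simulation.** 3,000 trials per scenario, N = 50, a 14-day baseline and nine 14-day treatment windows. Each subject's percent reduction is 100 × (1 − treatment rate/baseline rate). Three models are used: a common Poisson rate; lognormal subject rates with sigma 1; and the same lognormal rates with an independent gamma factor (k = 1) in each window. Entries are the mean over trials of the median percent reduction, in the order Poisson / lognormal / lognormal with k = 1. Repeat runs agree within about 1 point.

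| Rate per month | No effect, zeros dropped | True 50% reduction, zeros dropped | True 50% reduction, zeros scored as no change |
|---|---|---|---|
| 1 | 62 / 56 / 65 | 82 / 79 / 83 | 1 / 0 / 0 |
| 2 | 32 / 38 / 49 | 68 / 69 / 75 | 38 / 5 / 1 |
| 4 | 6 / 20 / 32 | 54 / 60 / 66 | 45 / 31 / 6 |
| 8 | −3 / 7 / 13 | 49 / 54 / 57 | 48 / 45 / 17 |
| 30 | −1 / −1 / −18 | 49 / 50 / 41 | 49 / 49 / 26 |

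**Longer baseline.** At 1 per month with no effect and zeros dropped, an 84-day baseline gives 3, 18 and 22%, and a 182-day baseline gives 1, 7 and 11%. More skewed models (sigma 1.5–2, k = 0.5) give 31–35% and 21–30%. A longer baseline therefore shrinks the artefact but does not always remove it.

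**Schedule A with the diary as baseline.** If a fraction f of subjects is on drug at screening and the true rate ratio is 0.5, the pooled ratio is 0.5/(0.5f + 1 − f). It is 0.5/1 = 0.50 at f = 0, 0.5/0.75 = 0.67 at f = 0.5, and 0.5/0.5 = 1.00 at f = 1. This does not depend on the seizure rate.

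**All-subject rate ratio.** Total treatment rate over total baseline rate, with zero-baseline subjects kept in, is 1.00–1.03 with no effect and 0.50–0.51 with a true halving (14-day baseline, 1–4 per month, all three models).

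**The case against.** Sections 1.0 and 11.2 agree with each other. The comparator is a historical rate, and the change from baseline in 11.2 most naturally refers to it. Section 5.4 does not say that the diary is the efficacy comparator. On that reading the two-week figures and the Schedule A dilution fall away. This stands as a limit on size. It does not supply a source or length for the historical rate or a zero rule, and it does not explain why 5.4 gives the diary the baseline role. The Data Dictionary cited in section 10.1 might define the rate, but it is not among the documents.

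The rates are assumed, and the gap between zero rules mostly closes at 8 per month and above. That also stands, except with overdispersion, where a true 50% reduction reads 57% or 17% at 8 per month.

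A reader might infer that two analysts following the text could report anything from near 0% to about 80% from the same diaries. The documents do not support that as a general statement. It needs about 1 seizure per month in the first two models (up to about 2 with overdispersion) and the diary as baseline. It also needs zeros to be scored as no change, a rule that appears nowhere in the text. Nor is interview recall a general alternative to the diary: it is tied to the ketogenic-diet safety waiver.

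**Conclusion.** Both gaps are in the text. The conflict over baseline holds at any seizure rate for subjects already on triheptanoin at screening. The missing zero rule matters in proportion to how short the baseline is and how rare seizures are. If the 14-day diary is used and zero-baseline subjects are dropped, the median can show a substantial reduction with no drug effect at 1–2 seizures per month. At 4 per month the false reduction is 6–32% depending on the model, and with a common rate it is gone by 8. Under a historical baseline of three to six months it is much smaller in the main models.

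These sizes rest on assumed rates and distributions, 50 subjects and complete diaries. Efficacy is a secondary objective with no planned test, and the primary safety analysis is untouched. The change should be made, ideally before efficacy data are summarised, but it does not put the trial's main purpose in question.

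**What to change.** 1. Reconcile sections 1.0 and 11.2 with 5.4. Use one pre-triheptanoin baseline, and record its source and start and end dates for each subject. Do not use the screening diary as baseline for subjects already on drug. The GLUT1 DS medical history taken at Screening may or may not hold a seizure rate: its footnotes (1 and 7) mention only confirmation of the diagnosis.
2. Keep the median percent reduction, labelled as covering subjects with baseline above zero. Beside it, give the number with a zero baseline and how many of them had seizures on treatment.
3. Add a treatment-versus-baseline seizure rate ratio over all subjects with a known baseline length, zero-baseline subjects included, with observation days as offset and a 95% confidence interval.
4. Report Schedules A and B separately, because their baselines differ in kind.

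The cost is a protocol amendment with IRB review (section 12.1) and a few data fields. Frequent seizers weigh heavily in the ratio: with lognormal sigma 1 the top 10% of subjects contribute Φ(1 − 1.2816) = 0.39 of seizures, so the median should stay beside it. In very skewed models with a 14-day baseline the ratio reads 1.06–1.13 under no effect, an error against the drug; at 84 days or more it is 0.99–1.01. Subjects with no dated baseline leave the ratio, possibly many in Schedule A. The ratio does not correct for enrolment during a bad spell or for changes in antiepileptic drugs.
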